10. EVALUATION OF QUALITY OF LIFE

The analysis of quality of life outcomes and health resource use will be performed on the FAS.

10.1 Health Related Quality of Life

Transitioning subjects (cohort 1) continue to use the HRQoL questionnaires used in the parent study, even if they transition to an older age group in this study. Newly recruited subjects (cohort 2) continue using the same HRQoL questionnaires used at their screening visit for this study, even if they transition to an older age group later in the study.

HR QoL assessments and the change from baseline to end of study will be summarized.

These tables will be created for the on-demand treatment only (i.e. subjects who received on-demand treatment exclusively over the whole study period), for the overall prophylaxis (combined standard, modified and PK-tailored prophylaxis) only as well as for subjects who received on-demand treatment and any prophylaxis treatment (i.e. subjects who switched during the study).

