### Planned Statistical Analysis

The Full Analysis Set (FAS) will be comprised of all subjects who are exposed to any amount of IP. For subjects who discontinue before reaching 100 EDs, data will be included up through the day of discontinuation. The FAS will be used for all analyses.

The pediatric (< 12 years) and the adolescent/adult ( $\geq 12$  years) data will be summarized separately, if appropriate. Further analyses will occur between the age cohorts < 6 years and 6 to < 12 years, if applicable.

Safety and efficacy data from the additional BAX326 naïve subjects (Cohort 2) will be analyzed together with the data from the previously treated subjects (Cohort 1).

The occurrence of IP-related AEs will be evaluated descriptively.

Frequency counts and percentages will be calculated for the following variables: occurrence of inhibitory and total binding antibodies to FIX, occurrence of antibodies to CHO proteins and rFurin, occurrence of severe allergic reactions (e.g., anaphylaxis), and occurrence of thrombotic events.

The following PK parameters for FIX will be reported using descriptive statistics:  $AUC_{0-\infty}$ , T1/2, MRT, CL, IR, and  $V_{ss}$ .

Incremental recovery (IR) will be summarized by visit and displayed graphically over time for each subject. Also the change from the baseline at screening visit will be described using summary statistics.

TGA parameters (lag time, time to peak thrombin generation, peak thrombin generation, and ETP) will be presented descriptively and displayed graphically. The efficacy of BAX326 in the treatment of bleeding episodes will be summarized. It includes the overall hemostatic efficacy rating at resolution of bleed, the number of infusions and the total weight-adjusted dose per bleeding episode.

The annualized rate of bleeding episodes (ABR) will be calculated by treatment regimen, only for subjects who have adequate treatment time for bleeding rate assessment.

Product consumption of BAX326 will be summarized, including the average number of infusions, the average weight-adjusted consumption per months and per year, as well as the average weight-adjusted consumption per event (prophylactic infusion and bleeding treatment).

HR QoL assessment and the change from the baseline will be summarized by visit. Analysis of patient activity level and pharmacoeconomic parameters will be descriptive in nature.

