**Table 13.2-1** depicts the specific domains within each instrument where potential differences over time due to the treatment may be expected. These should be considered as exploratory since it remains uncertain whether differences will be demonstrated and the study is not powered for these endpoints. Given that most subjects are moving from on-demand treatment to prophylaxis, and some patients will have longer than 6 months on prophylaxis, it is conceivable that differences might be seen.

Table 13.2-1 Potential Outcomes from HR QoL Measures		
Instrument	Description	Potential Change/Impact
SF-36 (patients 17 and older)  36 items	
The SF-36 is a validated, generic HR QoL instrument, measuring physical, emotional, social functioning as well as overall general health. It captures the following 8 domains:
 
Role Physical (RP)          Bodily Pain (BP)          Physical Functioning (PF)          General Health (GH)          Vitality (VT)          Social Functioning (SF)          Role Emotional (RE)          Mental Health (MH)
	
In this trial, differences may be demonstrated in the following domains:
 
 
1. Role Physical – This captures limitations in the kind of work or usual activities and reductions in amount of time spent on, or difficulty performing, work or other usual activities. With patients now receiving prophylaxis, they may be more willing to do activities that they may have avoided before in fear of a bleed.
 
2. Social functioning - This 2-item scale assesses the impact of physical and/or emotional problems on the quantity and quality of social activities. After 6 months on prophylaxis, patients may participate more in activities, such as sports that they might have avoided in the past, and thus, report improved social functioning as a result.
 
3. Bodily Pain - This assesses the intensity of bodily pain and the extent that pain interferes with normal work activities. It is not clear whether general pain will be reduced in 6 months, however, it may be shown that pain has not worsened over the 6 months on prophylaxis.
 

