Peds-QL  Parent-Proxy  Ages (years) 2-4, 5-7, and Child report 8-12 and 12-16 years old  23 items	
The Peds-QL is a generic HR QoL instrument designed specifically for a pediatric population. It captures the following domains:
 
Physical Functioning          Emotional Functioning          School Functioning          Social Functioning          Psychosocial Summary          Physical Health          Total Score
	
In this trial, differences in the following areas may be demonstrated:
 
 
1. Physical activities –Ability to do sports or other exercise, overall aches/pain, low energy
 
2. Emotional functioning – Worry about future/what will happen to self
 
3. Social functioning – Being able to participate in things other kids are doing
 
4. School functioning – Missing school due to doctor/hospital visit
 

Table 13.2-1 Potential Outcomes from HR QoL Measures		
Instrument	Description	Potential Change/Impact
Haemo-QoL (8-16 year olds)/Haem-A-QoL (17 and older)	
This instrument is a hemophilia-specific instrument that captures the following HR QoL domains:
 
 
Physical health
 
Feelings/emotional
 
View of self
 
Sports/leisure
 
School/work
 
Dealing with hemophilia
 
Treatment
 
Future
 
Family planning
 
Relationships
 
	
As a hemophilia-specific instrument, this measure assesses very specific aspects of dealing with hemophilia. Differences after 6 months of prophylaxis may be expected in many areas:
 
 
Physical health – Captures pain in joints, swelling pain, difficulty walking and needing extra time to prepare for activities.
 
Sports/leisure – Refrain from sports, restricted travel, needing to plan everything in advance
 
School/work – Everyday activities impeded due to hemophilia
 
Dealing with hemophilia –Ability to control bleeds
 
Future – Afraid of needing a wheelchair, worry about worsening condition, difficulty in leading a normal life
 

Haemo-QoL – 35 items		
Haem-A-QoL - 46 items		

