#### **14.3.2.4 Health-related Quality of Life and Pharmacoeconomics**

HR QoL assessments (SF-36/PedsQL, Haem-A-QoL/Heaemo-QoL, EQ-5D, and General pain assessment (VAS)), and the change from the baseline (at screening visit) will be summarized by visit. Analysis of patient activity level and health resource use will be descriptive in nature.

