3.2.4 Health-Related Quality of Life and Pharmacoeconomics

The assessment of HR QoL based on 4 questionnaires will be performed every 6 months ± 1 week. Newly recruited subjects will have their first HrQoL assessment including Patient Activity Level performed prior to or following the first infusion with BAX326, thereafter every 6 months.

The capture of health resource use will be performed by a named member of study site staff every 3 months ± 1 week. Newly recruited subjects will have their first health resource use capture prior to or following the first infusion with BAX326, thereafter at every 3 months ± 1 week.

Data on HR QoL and Health Resource Use will be collected using the instruments shown in the following table, with some instruments having an age specific version.

Table 1: Age specific instruments used for HR QoL and Health Resource Use

Instrument	Age Group (Age at the time of screening for Pediatric Study 251101 for Cohort 1 subjects or at the time of screening for Study 251001 for Cohort 2 subjects)			
	2 to 7 years	8 to 11 years	12 to 16 years	17 years and older
Leisure Time Exercise Questionnaire (Patient Activity Level)	Yes	Yes	Yes	Yes
Health Resource Use	Yes	Yes	Yes	Yes
Generic: PedsQL™	Yes: Parent-proxy versions (age groups: 2-4years and 5-7 years)	Yes: Child version	Yes	NA
Disease-specific: Haemo-QoL	NA	Yes: Short version	Yes: Short version	Yes
General pain assessment through a visual analog scale (VAS)	NA	NA	Yes	Yes
Health utility: EQ-5D	NA	NA	Yes	Yes
Generic: SF-36	NA	NA	NA	Yes

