5.5 Changes from the Planned Statistical Analysis in Protocol

The following changes from the planned statistical analysis in the protocol were made:

- In some instances, techniques will be used to adjust for missing data.
- In addition to the Full Analysis Set, a Per Protocol Analysis Set and a Pharmacokinetic Full Analysis Set were added.
- Pharmacokinetic parameters will be calculated using non-compartmental analysis (NCA), rather than a model combining data from this and previous studies, due to the lack of a suitable model.
- In order to determine the incremental recovery (IR) over time and see if antibodies have affected the recovery following long-term exposure, it is important to compare the end of study IR with the baseline IR. Therefore the IR will be summarized for baseline and end of study only rather than for all available time points.

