13. REVISION HISTORY

Version	Issue Date	Summary of Changes
1.0	26 Jul 2017	New Document
2.0	27 Sep 2017	
Section 6.6: Updated denominator for clarification and deleted compliance assessment regarding frequencies for modified prophylaxis since definition how data should have been captured was given insufficiently.
 
Section 9.1 and 11.2: IR and TGA will be summarized for baseline and end of study only rather than for all available time points.
 
Minor updates for clarification throughout the whole document.

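### SAP 10.1 gives HR QoL change from baseline only to end of study, where the protocol plans it at each six-monthly visit, and SAP 5.5 does not declare the difference

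*SAP*

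**What the plan says.** **Protocol.** Section 14.3.2.4 names the instruments and continues: "and the change from the baseline (at screening visit) will be summarized by visit". The synopsis agrees: "HR QoL assessment and the change from the baseline will be summarized by visit". Evaluating changes in HR QoL is a study objective (7.2), and the scores are listed among the secondary outcome measures (8.3.2.4).

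**Schedule.** SAP 3.2.4 repeats the protocol's timing: "The assessment of HR QoL based on 4 questionnaires will be performed every 6 months ± 1 week".

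**SAP analysis.** Section 10.1 says: "HR QoL assessments and the change from baseline to end of study will be summarized". Its tables are split by regimen history (on-demand throughout, prophylaxis throughout, switched), with no visit dimension. SAP section 5 pools the two cohorts and leaves section 10 out of the age-group splits.

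**Declared changes.** SAP 5.5 lists four departures from the protocol. One is the same kind of narrowing for incremental recovery, with a reason given: "Therefore the IR will be summarized for baseline and end of study only rather than for all available time points". The revision history, for sections 9.1 and 11.2, says: "IR and TGA will be summarized for baseline and end of study only rather than for all available time points". Neither place mentions HR QoL or section 10.1.

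**Expected timing of change.** On the haemophilia-specific instrument, protocol Table 13.2-1 says: "Differences after 6 months of prophylaxis may be expected in many areas". The text introducing that table qualifies its contents: "These should be considered as exploratory since it remains uncertain whether differences will be demonstrated and the study is not powered for these endpoints".

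**The concern.** Followed as written, the SAP yields one change-from-baseline summary per instrument and regimen group, taken at each subject's last assessment. The protocol planned a series of them. The section that exists to list such departures covers a parallel one and omits this one, so a reader of the study report would not know that a planned table had gone.

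The single time point that is kept is also hard to interpret. End of study depends on licensure in the subject's country and on accumulated exposure days, so it falls at different follow-up times for different subjects. All naive subjects receive prophylaxis, so in the prophylaxis table their changes sit alongside those of transitioning subjects who may have been followed for several years. The neighbouring section 10.2 allows for unequal follow-up by reporting health resource use per subject-year. Section 10.1 has no counterpart.

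**Working it through.** There is no power or alpha figure to reproduce: both documents say that the sample size does not rest on statistical considerations. The check is a comparison of text plus simple arithmetic on follow-up.

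**1. Side by side.**

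| Item | Protocol 14.3.2.4 and synopsis | SAP 10.1 |
|---|---|---|
| Scores | by visit | summarised, time points not stated |
| Change from baseline | by visit | to end of study |
| Listed in SAP 5.5 | – | no |

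Only the change row is a clear departure. The scores row is open to interpretation.

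**2. How far apart end-of-study times can be.** Inputs: about 100 exposure days for naive subjects (protocol 8.2), two infusions per week (standard prophylaxis), a ceiling of 68 months (protocol 8.2), and 30.44 days per month.

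- Time to 100 exposure days = 100 / 2 = 50 weeks; 50 × 7 / 30.44 = 11.5 months.
- Ratio of ceiling to nominal = 68 / 11.5 = 5.9.

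The infusion rate is an assumption for subjects on other regimens. Over an assumed range:

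| Infusions per week | Months to 100 exposure days | 68 / months |
|---|---|---|
| 1 | 23.0 | 3.0 |
| 2 | 11.5 | 5.9 |
| 3 | 7.7 | 8.9 |

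Subjects who withdraw early are included up to withdrawal (SAP 5.2), which adds shorter times.

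**3. Planned time points lost.** 68 / 6 = 11.3, so a subject followed to the ceiling has up to 11 scheduled six-monthly assessments, plus the completion visit. SAP 10.1 specifies a change at one time point.

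**4. Baseline.** The protocol takes baseline at screening; SAP 5.3 takes the last value before the first infusion of product. For Cohort 1, Table 21.2-1 marks no HR QoL at screening, and the Cohort 1 screening list in Table 21.1-1 does not include it. The source of their baseline is therefore unstated. The end-of-study change needs it just as much as a by-visit change does.

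**5. What Month 6 means.** In the pivotal study 59 of 73 subjects received prophylaxis, and in the paediatric study all 23 did: (59 + 23) / (73 + 23) = 82 / 96 = 85% of parent-study subjects. Among the 56 pivotal subjects analysed for prophylaxis, median treatment was 6 months. Screening here is on the day of the parent-study termination visit. For most of Cohort 1, Month 6 of this study is therefore not the first six months on BAX326 prophylaxis. For Cohort 2 it is the first six months on BAX326.

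**The case against.** The best defence is that SAP 10.1 is loosely worded and was not meant as a cut. It names two things, the assessments and the change to end of study, and the first is not limited to any visit. Where the SAP restricts time points deliberately, it says so with the word *only*, as for recovery and TGA, and the revision history does not name 10.1. This stands in part: scores at each visit may already be intended. It does not rescue the change, which is tied to end of study and nothing else.

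A second defence is that the outcome is descriptive, exploratory in its expectations and unpowered. That limits what can be concluded, but it does not cancel a planned table.

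A third is that the spread in follow-up sets a nominal case against a ceiling. That is correct. The protocol synopsis and 8.1.2 keep naive subjects until licensure or 100 exposure days, whichever is later, so some may stay longer than 11.5 months. The SAP also reports medians, quartiles and ranges alongside means. The times still differ by design.

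Four stronger readings are tempting but not supported:

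- *The SAP discards the six-month effect the protocol predicts.* Table 13.2-1 says that differences may occur, and most of Cohort 1 had prophylaxis before entry.
- *No Month 6 output exists at all.* Scores may be covered.
- *By-visit tables would separate treatment from ageing.* The study is uncontrolled, so they would not, and no figure in the documents shows a particular problem in children.
- *The narrowing was data-driven.* The SAP versions date from July and September 2017, after the planned cut-off of 31 December 2016, but nothing in the documents links the wording to results.

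**Conclusion.** The point holds, as a minor one. The protocol plans HR QoL change from baseline at each six-monthly visit. SAP 10.1 specifies it only to end of study, and SAP 5.5 is silent although it declares the parallel restriction for recovery.

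A pooled change to end of study does not describe change over time, because end of study ranges from nominally 11.5 months to a ceiling of 68. That contrast assumes twice-weekly dosing and stopping at 100 exposure days for the shorter figure. The ratio is about 5.9 under that assumption and 3.0 to 8.9 for one to three infusions per week. The actual distribution of follow-up is not in the documents, so these figures show what is possible and not what occurred. The primary outcome, adverse events related to product, is unaffected.

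**What to change.** In SAP 10.1:

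- Summarise score and change from baseline at each six-monthly visit, with n per visit. Late visits with few subjects may be collapsed or only listed.
- Keep end of study as an added row, with the follow-up time to that assessment shown.
- Use the same baseline for the by-visit and end-of-study changes, and state where it comes from for Cohort 1.
- Note that Month 6 is the first six months on BAX326 for Cohort 2 only.

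If the restriction to end of study is intended, declare and justify it in SAP 5.5, and say whether scores are tabulated at every visit.

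No new data are needed. The cost is a larger set of descriptive tables. For adults, the 8 SF-36 domains and the 10 listed domains of the haemophilia-specific instrument make 18; at up to 11 visits that is 18 × 11 = 198 rows per regimen group, before EQ-5D and the pain scale. Collapsing the sparse late visits would cut this considerably.

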10.2 Health Resource Use

The analysis of health resource use will be descriptive in nature. The total number of hospitalizations, emergency room visits, unscheduled physician office visits and days missed from work/school will be reported. Additional analyses include mean hospitalizations per subject, mean length of stay and mean number of days missed from work/school.

These tables will be created per subject year for the on-demand treatment only (i.e. subjects who received on-demand treatment exclusively over the whole study period), for the overall prophylaxis (combined standard, modified and PK-tailored prophylaxis) only as well as for subjects who received on-demand treatment and any prophylaxis treatment (i.e. subjects who switched during the study).

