**Please note:**

*The dose and dosing frequency should be adjusted according to the individual subject's age, the number of breakthrough bleeds and/or the subject's physical activity.*

*It is recommended to administer prophylactic infusions prior to weekdays with increased physical activity.*

*In subjects with severe hemophilic arthropathy and/or target joints who continue experiencing recurrent bleeding episodes despite adjustments of the prophylactic dose and/or dosing frequency, an ultrasound of the affected joint(s) should be performed to verify the presence of a bleed.*

Dose and/or frequency adjustments should be performed if a subject meets either of the following criteria:

- **Two or more spontaneous** (not related to trauma) bleeding episodes in the same target joint within any 3-month period, **OR**
- **One or more spontaneous** (not related to trauma) bleeding episodes in a non-target joint or a non-joint within any 3-month period

In such a case, the dose and/or frequency will be increased. The dose is not to exceed 100 IU/kg and an increase in frequency should be considered. It is recommended to consult the sponsor.

The regimen should preferably be maintained until the end of the study, unless clinical circumstances or the subject's wish necessitate a change as described above. Any change in the regimen, and the reason for such change, will be recorded in the eCRFs.

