EQ-5D 6 items	
This instrument captures overall HR QoL; a health utility score can be calculated from this measure. There are adult and proxy versions. It captures physical, mental, and social functioning.
	
The primary reason to administer this instrument is to obtain health utility data, which may serve for input into a cost-effectiveness analysis, in case a cost-effectiveness model is developed.

VAS General Pain Assessment 1 item	
This is a VAS that assesses general pain over the past 4 weeks.
	
While a reduction in acute pain due to a bleed may be expected, it is uncertain whether 6 months of prophylaxis treatment will be able to reduce general, chronic pain in this patient population.

Leisure Time Exercise Questionnaire	
This question captures intensity and frequency of exercise over one week.
	
This will allow an understanding of patient activity levels in our trial population and test for an association between ABR and patient activity level.

Table 13.2-1 Potential Outcomes from HR QoL Measures		
Instrument	Description	Potential Change/Impact
Health resource use items 4 items	
This information will be gathered by the sites as part of the eCRF, subjects will not have to complete a questionnaire.
 
It assesses:
 

• Number of days missed from work/school

• Number and days of hospitalizations

• Number of emergency visits to a hospital

• Number of unscheduled visits to a general practitioner

	This information is necessary to collect as input into a cost-effectiveness analysis that may be developed in the future.

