5. STATISTICAL CONSIDERATIONS

Safety, efficacy, PK, HRQoL and immunogenicity data from the additional BAX326 naïve subjects (Cohort 2) will be analyzed together with the data from the previously treated subjects (Cohort 1).

The pediatric (< 12 years) and the adolescent/adult (≥ 12 years) data (i.e. age group 1) will be summarized separately and overall for all outcome measures except for analyses mentioned in section 10, section 11 and pharmacokinetic analyses (it turned out that only adults underwent an abbreviated PK study). Further analyses will occur between the age groups <6 years, ≥ 6 to <12 years, ≥ 12 to <18 and ≥ 18 (i.e. age group 2) for all outcome measures except for analyses mentioned in section 10, section 11.1 and pharmacokinetic analyses.

In case it is specified that analyses for a specific outcome measure will also be presented by treatment regimen, the summary statistics should be presented by individual treatment regimen (standard prophylaxis, modified prophylaxis, PK-tailored prophylaxis and on-demand treatment) as well as for overall prophylaxis (combined standard, modified and PK-tailored prophylaxis).

If a subject changes regimen during the course of the study, then the data from that subject will be analyzed under the initial allocated regimen until a change of regimen is recorded. Data recorded after this stage will be analyzed under the updated regimen.

In general, all efficacy, safety, PK, HRQoL and immunogenicity variables will be summarized using descriptive statistics. Continuous variables will be summarized by sample size [n], mean, standard deviation [SD], median, minimum, maximum, Q1 and Q3. Categorical variables will be summarized in frequency tables (n, frequencies, and percentages). Additional statistics which will be provided for specific endpoints will be described in the corresponding section.

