7.2.2 Prophylaxis: Annualized Bleed Rate

The ABR will be calculated as follows:

$$\frac{\text{Number of bleeding episodes}}{\text{Observed treatment period in days}} * 365.25.$$

The ABR will be listed and summarized only for subjects who have adequate treatment time for bleeding rate assessment. For subjects on prophylaxis, a subject is considered to have an adequate treatment time for bleeding rate assessment if the observation period with BAX326 in this study within the respective treatment regimen was a minimum of 3 months (treatment period for surgery and bleeding period are not counted).

The observation period for prophylactic treatment is considered as the time between the first and the last prophylactic infusions. For transitioning subjects, infusions prior to eligibility assessment will count in case the treatment regimen is the same as the regimen the subject receives after eligibility is confirmed. The treatment period for surgery as well as the bleeding period will be excluded from the calculation of observation period in the calculation.

Additionally, the ABR will also be calculated for subjects with on-demand treatment. The observation period for on-demand treatment is considered as the time between the date of eligibility (or the date of switching to on-demand for subjects who were on prophylaxis before) and the end of observation period.

These tables will be created by treatment regimen.

ABR will be also presented by bleeding site (joint/non-joint), cause (spontaneous/injury), severity (minor, moderate, major, and life/limb-threatening), presence of target joints and FIX activity levels at screening. These subgroup analyses will be performed on the FAS only.

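### SAP 10.2 sorts health resource use per subject-year by whole-study treatment history, so no column gives the rate for all time on a regimen

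*SAP*

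**What the plan says.** SAP 10.2 plans descriptive totals and means for hospital stays, emergency visits, unscheduled physician visits and missed work or school days. On layout it states: "These tables will be created per subject year for the on-demand treatment only", with that group defined as "subjects who received on-demand treatment exclusively over the whole study period". The other groups are prophylaxis only (standard, modified and PK-tailored combined) and "subjects who received on-demand treatment and any prophylaxis treatment (i.e. subjects who switched during the study".

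SAP 5 sets a general rule for a subject who changes regimen: "data from that subject will be analyzed under the initial allocated regimen until a change of regimen is recorded". After the change, "Data recorded after this stage will be analyzed under the updated regimen".

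SAP 7.2.2 tabulates the annualized bleeding rate by regimen. For on-demand treatment, observation can start at "the date of switching to on-demand for subjects who were on prophylaxis before".

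On the data, Protocol 8.6.3.1 states: "Any change in the regimen, and the reason for such change, will be recorded in the eCRFs". SAP 3.2.4 has resource use captured every 3 months. On purpose, Protocol Table 13.2-1 says of these items: "This information is necessary to collect as input into a cost-effectiveness analysis". The same sentence adds that such an analysis may be developed in the future.

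**The concern.** A rate per subject-year describes time spent in a state. SAP 10.2 decides which time counts by looking at what the subject did afterwards. Someone who spends two years on demand and then starts prophylaxis adds nothing to the on-demand rate. Those events and years go to the third column together with the prophylaxis time. The prophylaxis-only column is conditioned in the same way.

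Two things are at stake. First, if the decision to switch is related to resource use, the single-regimen columns are selected on the outcome they report. Second, the third column averages two regimens in proportions set by when people switched, so it cannot be read as a rate on either. On-demand bleeding rates and on-demand resource use in the same report would also rest on different subjects and different time.

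**Working it through.** The plan gives no rate, number of switchers or sample-size basis for this outcome, so there is no figure to reproduce. The check traces where time goes and then sizes the gap under stated assumptions.

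**1. Attribution.** Take a subject with 2 years on demand followed by 1 year on prophylaxis.
- SAP 5 rule: 2 years to on-demand, 1 year to prophylaxis.
- SAP 10.2: 0 years to on-demand, 0 to prophylaxis only, 3 to the switched group.

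Moves among standard, modified and PK-tailored prophylaxis stay inside one column. Only switches between on-demand and prophylaxis matter here.

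**2. Size if switching is related to use.** Let p be the share of on-demand starters who switch, f the fraction of follow-up they spend on demand first, and R their on-demand use relative to never-switchers. Follow-up is taken as equal. Then

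on-demand column / rate over all on-demand time = [(1-p) + p·f] / [(1-p) + p·f·R].

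All values of p, f and R are assumptions.

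| p | f | R | Ratio | Column too low by |
|---|---|---|---|---|
| any | any | 1 | 1.00 | 0% |
| 0.25 | 0.25 | 1.5 | 0.8125/0.84375 = 0.96 | about 4% |
| 0.25 | 0.5 | 1.5 | 0.875/0.9375 = 0.93 | 7% |
| 0.5 | 0.5 | 2 | 0.75/1.00 = 0.75 | 25% |
| 0.5 | 0.5 | 3 | 0.75/1.25 = 0.60 | 40% |

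**3. The pooled column.** Assume 14 on-demand starters followed for 3 years, of whom 4 switch after 1 year. Never-switchers use 0.5 per year. Switchers use 1.5 per year before the switch and 0.5 after.
- SAP on-demand column: 0.50 per year.
- All on-demand time: (10×3×0.5 + 4×1×1.5) / (10×3 + 4×1) = 21/34 = 0.62 per year. Ratio 0.81.
- Switched column: (1×1.5 + 2×0.5)/3 = 0.83 per year, which is the switchers' rate on neither regimen.

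**4. Simulation.** Assumptions: quarterly visits, a mean of 1.0 event per year on demand and 0.5 on prophylaxis, 2 or 4 years of follow-up, and between-subject (gamma frailty) variance of 0, 0.5 or 1. The chance of switching each quarter depends on whether an event occurred in it.

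| Switch chance per quarter: no event / event | Share switching | Column / all on-demand time |
|---|---|---|
| 3% / 3% | 19-37% | 1.00 |
| 1% / 5% | 12-25% | 0.93-0.97 |
| 1% / 10% | 18-37% | 0.84-0.94 |
| 2% / 20% | 32-60% | 0.68-0.87 |
| 2% / 40% | 46-81% | 0.42-0.71 |

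With no between-subject variance, the split rate recovers 1.00 under event-related switching while the SAP column gives 0.69 to 0.97. Conditioning on never switching is therefore enough to bias the column. With between-subject variance the split rate also falls below 1.0 (0.72 at the most extreme setting), because heavy users leave on-demand early. Splitting corrects the attribution of time; it does not adjust for who leaves.

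**The case against.** The strongest defence is that 10.2 states its own specific grouping, and SAP 9.1, 10.1 and 11.2 use the same kind of history groups, so this looks deliberate. Switchers are not lost; they have a labelled column. Protocol 14.3.2.4 promised only a descriptive analysis, so nothing promised there is broken. All of this stands. But history groups suit a change from baseline to end of study better than a rate per subject-year, and the labelled column cannot be separated back into regimens. SAP 5 names section 10 as an exception to the age-group summaries but not to the regimen-change rule.

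A reader might infer more than the documents support:
- *The planned on-demand rate is biased low.* The direction is assumed. The bleed-triggered adjustment criteria in Protocol 8.6.3.1 and Table 21.1-1 concern prophylactic regimens. A regimen may also change at the subject's wish, and SAP 7.2.2 provides for moves from prophylaxis to on-demand.
- *Switching within this study is common.* Protocol 13.2 speaks of most subjects moving from on-demand to prophylaxis, but does not place that move within this study. In the pivotal study 59 of 73 were already on prophylaxis.
- *The rate could be half the true one.* In the formula with p = 0.5 and R = 3, that needs f = 1, meaning switchers stay on demand to the end of follow-up.
- *Each switcher is about 7% of the on-demand group.* The 14 on-demand subjects (1/14) belong to the pivotal study; the number in this study is not given.
- *A planned cost-effectiveness analysis will be misled.* It is only a future possibility, and subject-level data could still be split then.

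**Conclusion.** The point holds as one of interpretation. As laid out, SAP 10.2 gives no resource-use rate for all time on a regimen, and it departs without a stated reason from the SAP 5 rule and from the approach in 7.2.2. Bias in the single-regimen columns is conditional on switching being related to use. If heavier on-demand users switch, the on-demand column is about 4-40% too low over p = 0.25-0.5, R = 1.5-3 and f = 0.25-0.5. Stronger event-driven switching gives larger gaps, and unrelated switching gives none. For the prophylaxis-only column, and for moves from prophylaxis to on-demand, the direction cannot be stated. No test or primary outcome is affected. This is a worthwhile improvement rather than a necessary one.

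**What to change.** In SAP 10.2, allocate events and subject-years to the regimen in force under the SAP 5 rule, using the recorded regimen changes. Assign a 3-month interval that contains a switch, with both its events and its time, to the regimen in force at the start of the interval. Add a sensitivity table that excludes such intervals. Starting-regimen assignment is preferable to giving the interval to whichever regimen was held longer, because the latter can move events that came before a switch into the later regimen. Keep the three history groups as a supplementary table and report the number of switchers in each direction.

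The cost is SAP wording and a split of subject-time. No new data are needed, provided the recorded changes carry dates and cover moves between on-demand and prophylaxis, as SAP 5 and 7.2.2 presuppose. The small downside is that events in switch intervals are allocated only approximately.
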